5.11 Study Medication Use, Patient Instructions and Diary

Each subject’s drug kit box contains █████ 0.47 gram tubes. At the baseline visit, the subject will apply the contents of one of the tubes at the site under study staff supervision and that tube will be placed back in the drug kit box. The second tube will be given to the subject to take home with them for their second application along with a diary. Their Day 2 application should be applied at approximately the same time as the Day 1 application. Additionally, the study staff must ensure subjects understand the instructions for applying the study medication and refrigerate the study medication at home all times.

Subjects must not use the study medication for more than 2 consecutive days.

At Visit 2/Day 3 the study medication will be collected to visually assess compliance. Compliance will also be determined from the diary, in which the subject will be instructed to record if they applied their second dose of medication or not. After the compliance evaluation, empty, filled and partially used tubes will be collected and kept by the site.

Subjects will wash the designated treatment area with a mild soap by using only the hands and pat dry with a soft towel █████ before applying the study medication. The study medication from one tube will be applied to the selected treatment area, one contiguous skin area of 25 cm² area. After spreading the study medication █████ over the treatment area, █████. Subjects should wash their

hands with mild soap and water immediately after applying the study medication gel and take care not to transfer the applied study medication gel during and after application to other areas, including the eyes. If the treatment area is on the back of the hands (not palm), the subject should wash only the fingertip which was used for applying the gel. [REDACTED]

[REDACTED]

Subjects will be instructed to not use any other topical treatments or products other than the study medication gel or approved moisturizer in the selected treatment area during the two-day treatment period.

Diaries will be dispensed for each enrolled subject. The subjects will be instructed to complete their diary after applying the subsequent dose of study medication. At Visit 2/Day 3, the study personnel will review the diary to determine subject dosing compliance, confirm use of any prohibited medications, assess AEs and a new diary will be dispensed to all subjects. At each subsequent visit, study personnel will review the diary card to determine if the subject used any prohibited medications, assess AEs and dispense a new diary (a diary will not be dispensed at Visit 4/ Day 57). In addition, each study subject will be reminded to return the previously dispensed tube (regardless of content) at Visit 2/Day 3 and the completed diary at the next visit. Study personnel will schedule the subject's next visit prior to the subject's departure.

5.12 Visit Specific Procedures

The following sections outline the procedures required at each visit.

5.12.1 Visit 1/Day 1 (Baseline)

Prospective subjects will visit the study center and will be examined by the principal investigator or delegated staff. The following procedures will be performed at the baseline visit:

- [REDACTED]

[REDACTED]

- █ [REDACTED]
- █ [REDACTED]

5.12.2 Visit 2/Day 3 (± 1 day)

- █ [REDACTED]

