2.2 Safety

Safety of the test and reference products will be compared by evaluating the nature, severity and frequency of their adverse event profiles. All adverse events that occur during the study (from the moment a subject signs an informed consent/assent) will be recorded. Descriptions of reactions or complaints will include the approximate date of onset, the date the adverse event ended, the severity of the adverse event, and the outcome. Comparisons between the treatment groups will be made by tabulating the frequency of subjects with one or more adverse events (classified into MedDRA terms) during the study. Pearson's Chi-Square test or Fisher's Exact test, whichever is most appropriate, will be used to compare the proportion of subjects in the two active treatment groups with any adverse event. [REDACTED]

Protocol No: PRG-NY-15-002

of the subject's adverse events (AEs). At this visit, the Follow-Up Telephone Call/Day15, Visit 3/Day 29 and Visit 4/Day 57 will be scheduled.

A Follow-Up Telephone Call will be made by study staff to the subject at Day 15 to review and assess subject compliance (diary completion), record AEs, update concomitant medication use, and to remind the subjects of the protocol requirements and next study visit schedule.

At Visit 3/Day 29 (Interim) and Visit 4/Day 57 (End of Study), subjects will be asked if they experienced any adverse events, taken any concomitant medications and generally complied with protocol requirements. The diary dispensed at Visit 2 will be collected and reviewed with the subject, and a new diary will be dispensed at Visit 3/Day 29. The diary dispensed at Visit 3 will be collected and reviewed at Visit 4/Day 57. Safety will be assessed by the monitoring of all adverse events (AEs) and clinically significant changes from Visit 1/Day 1 (Baseline) and an application site reaction assessment will be conducted at Visit 3/Day 29 and Visit 4/Day 57.

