5.10 Application Site Reaction Assessment

To the greatest extent possible, the same investigator who made Visit 1/Day 1 (Baseline) assessments will assess the application site reactions, grade them according to a 5-point scale and a designated staff will record them in the source document and eCRFs at each subsequent visit. This assessment must be conducted by qualified individuals listed on the Form FDA 1572 who have been delegated this task by the PI. [REDACTED]

At baseline (prior to initial dosing) and each subsequent visit, application site reactions of erythema, flaking/scaling, crusting, swelling, vesiculation/pustulation, and erosion/ulceration are to be recorded in the source document and eCRFs.

Application site reactions (erythema, flaking/scaling, crusting, swelling, vesiculation/pustulation, and erosion/ulceration) are not to be recorded as adverse events unless they result in either:

- The temporary discontinuation of the study medication.
- The discontinuation of the subject from the study.
- The use of a new concomitant medication in order to treat this event.

Any other application site reaction not listed above (such as pain, pruritus and infection) should be recorded as adverse events in the source document and eCRFs.

The following scale will be used for the Application Site Reaction Assessment:

Site Reaction	Description
Erythema	[REDACTED]
Flaking/scaling	[REDACTED]
Crusting	[REDACTED]
Swelling	[REDACTED]
Erosion/ulceration	[REDACTED]
Vesiculation/Pustulation	[REDACTED]

Site Reaction	Grading Criteria				
	0	I	I	I	I
██████████	██████████	██████████	██████████	██████████	██████████
██████████ ██████████	██████████	██████████ ██████████	██████████	██████████	██████████ ██████████
██████████	██████████	██████████	██████████	██████████	██████████ ██████████
██████████	██████████	██████████ ██████████	██████████ ██████████ ██████████	██████████ ██████████	██████████ ██████████ ██████████
██████████ ██████████	██████████	██████████ ██████████	██████████ ██████████ ██████████	██████████	██████████ ██████████
██████████ ██████████	██████████	██████████	██████████ ██████████ ██████████	██████████ ██████████ ██████████	██████████ ██████████ ██████████ ██████████

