5.12.4 Visit 3/Day 29 (± 3 days)

- █ [REDACTED]

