To compare the safety and efficacy profiles of Perrigo New York, Inc.'s Ingenol Mebutate Topical Gel 0.05% to Picato® Topical Gel 0.05% (Ingenol Mebutate Topical Gel 0.05%) and to demonstrate the superior efficacy of the two active formulations over that of the vehicle in the treatment of Actinic Keratosis.

3 Study Design

For the purpose of exploring the above objectives, the study will be conducted as a double-blind, randomized, parallel-group, vehicle-controlled, multicenter trial.

Each subject will be randomly assigned to one of following treatment groups :

- (1) Test: Ingenol Mebutate Topical Gel 0.05%, Perrigo New York, Inc.
- (2) Reference: Picato® Topical Gel 0.05% (Ingenol Mebutate Topical Gel 0.05%), Leo Pharma Inc.
- (3) Vehicle of test product, Perrigo New York, Inc.

Subjects will be admitted into the study only after written informed consent has been obtained and all of the inclusion and none of the exclusion criteria have been met. Randomization will be performed according to a computer generated randomization scheme where the treatment group designation has been assigned to the subject number. The treatment designation will remain blinded until the final database is closed. An independent third party will generate and hold the randomization code throughout the study. Randomized subjects will apply assigned

topical gel [redacted] once daily for two (2) consecutive days to the selected treatment area (one contiguous skin area of approximately 25cm² treatment area on the trunk/extremities) avoiding contact with the eyes, mouth and other body areas during and after gel application.

Subjects will be scheduled for an office visit for Visit 1/Day 1 (Baseline), Visit 2/Day 3 (±1 days) (Post-Treatment Interim), Visit 3/Day 29 (±3 days) (Interim), and Visit 4/Day 57 (±2 days) (End of Study). Safety will be assessed by monitoring adverse events at each visit and during a Follow-Up Phone Call/Day 15 (±3 days).

4 Populations To Be Analyzed

Three subject populations are defined as follows:

- (1) An intent-to-treat (ITT) subject is any individual who: (a) was randomized into the study, and (b) received and applied at least one dose of study medication;
- (2) A modified intent-to-treat (mITT) subject is any individual who: (a) was randomized into the study, (b) met eligibility criteria, (c) received and applied at least one dose of study medication, and (d) had at least one post-baseline efficacy assessment;

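### Minor: the Visit 2 window of Day 3 ±1 day includes Day 2, the day of the second dose, although the visit is meant to follow treatment

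*Protocol*

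**What the plan says.** **Window.** The protocol heading for the visit is "5.12.2 Visit 2/Day 3 (± 1 day". SAP section 3 lists the same visit as "Visit 2/Day 3 (±1 days) (Post-Treatment Interim". The protocol's table of contents prints this heading with +1 day instead, but the body heading and the SAP agree with each other and are the operative text.

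**Dosing.** There are two doses. The first is applied at the site on Day 1 and the second at home: "Their Day 2 application should be applied at approximately the same time as the Day 1 application" (Protocol 5.11). Under Protocol 5.16 a subject who misses either dose is non-compliant.

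**What happens at Visit 2.** Protocol 5.11 states: "At Visit 2/Day 3 the study medication will be collected to visually assess compliance". The diary, in which the subject records whether the second dose was applied, is reviewed at the same visit. Protocol 5.10 sets the timing of reaction grading: "At baseline (prior to initial dosing) and each subsequent visit, application site reactions of erythema" and five further listed reactions are recorded.

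**The next contacts.** The visit narrative just before Protocol 3.2 says: "A Follow-Up Telephone Call will be made by study staff to the subject at Day 15". The next office visit is "5.12.4 Visit 3/Day 29 (± 3 days".

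**How the grades are used.** Under Protocol 5.10 the six listed reactions "are not to be recorded as adverse events unless they result in either" a temporary stop of the medication, withdrawal from the study or a new concomitant medication. Protocol 8.1.5 has test and reference compared descriptively on these reactions. SAP 5.6 tabulates their severity by treatment group and visit.

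**The concern.** The lower limit of the window falls on a dosing day. Everything the visit is for presumes that dose 2 has already been applied: the SAP's label, the return of the tube and the check on the second application. A visit held early on Day 2 could serve none of these purposes properly. One held later that day would meet the compliance purpose but would grade the skin only hours after the dose.

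What is at stake is the clarity of one safety table. Most listed reactions will not appear as adverse events, so the by-visit grades are the main visible record of acute local tolerability for test against reference. Day 2 grades would be pooled in the Visit 2 row with grades taken one or two days after the completed course. No visible rule separates them. The tube might also be collected before the second dose was due.

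**Working it through.** The check is day arithmetic. No sample size, power or alpha figure is involved.

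**Inputs.** Visit 2 at Day 3 ± 1 (Protocol 5.12.2, SAP 3). Doses on Days 1 and 2 at about the same clock time (Protocol 5.11). Visit 3 at Day 29 ± 3 (Protocol 5.12.4, SAP 3).

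**Step 1: the window as written.** 3 − 1 = 2 and 3 + 1 = 4, so Days 2, 3 and 4 are all in window. Day 2 is the second-dose day.

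**Step 2: time since dose 2, and the wait for the next scheduled grade.** Visit 3 spans 29 − 3 = Day 26 to 29 + 3 = Day 32. Nominal hours since dose 2 are 24 × (visit day − 2), taking the visit at the dosing clock time. Days to the next grade are 26 − visit day to 32 − visit day.

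| Visit 2 held on | Nominal time since dose 2 | Days to Visit 3 grade |
|---|---|---|
| Day 2 | 0 h (in practice before dose 2, or hours after it) | 24 to 30 |
| Day 3 | 24 h | 23 to 29 |
| Day 4 | 48 h | 22 to 28 |
| Day 5 (outside the present window) | 72 h | 21 to 27 |

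Only the Day 2 row can precede dose 2.

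**Step 3: what a later lower limit changes.**
- Day 3 (+1 day) gives Days 3 to 4: nominally 24 to 48 h after dose 2, with 22 to 29 days to the next grade.
- Day 3 (+2 days) gives Days 3 to 5: nominally 24 to 72 h, with 21 to 29 days to the next grade.

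Either removes the dosing day. Neither does much to the long wait for Visit 3, which comes from the visit schedule and not from this window.

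**Step 4: can the effect on the table be sized?** If a share f of subjects is graded on Day 2, with reaction frequency p1, and the rest later, with frequency p2, the Visit 2 row shows (1 − f) × p2 + f × p1. It therefore differs from p2 by f × (p2 − p1). The documents give neither f nor p2 − p1, so this cannot be evaluated.

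**Step 5: could Day 2 visits plausibly occur?** ASSUMPTION, not in the documents: clinics open on weekdays only. After a Thursday baseline, Days 2, 3, 4 and 5 are Friday, Saturday, Sunday and Monday. Under ±1 the only usable day is Friday, Day 2. Under +1 there is none. Under +2 there is Monday, Day 5. For a baseline from Monday to Wednesday, Day 3 is a weekday. For a Friday baseline, Day 4 is a Monday.

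**The case against.** **The deciding text may be hidden.** The Visit 2 procedure list (Protocol 5.12.2) and both schedule tables (Protocol 5.13, SAP 6.2) are blacked out, as is text next to the dosing rules in Protocol 5.16 and 8.1.1. The start of the visit narrative is missing. An instruction that dose 2 comes before the visit could be in any of these places. This stands as a limit on certainty. It does not remove the point: a dose-first rule would still permit a grade within hours of dose 2, and a hidden bar on Day 2 visits would contradict the window printed in both documents.

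**Visible text already implies that dose 2 comes first.** The subject completes the diary after dosing, and staff inspect the returned tube. A careful site would probably hold a Day 2 visit after the dose. This stands in part: the realistic case is a grade taken hours after dose 2 more often than one taken before it.

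**The consequence is small.** The reaction comparison is descriptive, the trial is randomized and double-blind so that visit timing should balance across arms, and unscheduled visits are allowed. Pain, pruritus and infection at the site are recorded as adverse events, as are listed reactions that lead to a new medication, an interruption or withdrawal. All of this stands and is why the point is minor.

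**A +1 window can be unworkable.** On the weekday assumption, a Thursday baseline has no permitted visit day under +1. This stands against +1 but is met by +2.

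**Conclusion.** The point holds as a minor design inconsistency. The stated window admits the second-dose day for a visit described as post-treatment, at which second-dose compliance is checked and the only visible scheduled reaction grade before Visit 3 is taken. That conclusion rests on the two matching window statements and on day arithmetic. It is subject to the reservation that redacted text may govern the order of dose and visit.

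Three stronger readings are tempting, and the documents do not support them:
- A reader might infer that the Visit 2 row will understate reactions by some number of percentage points, or shrink a test-reference difference. No visible text says when reactions appear or peak, or how many visits will fall on Day 2. Any such figure would be assumed input returned as output.
- A reader might blame the window for the three to four weeks without a scheduled grade. That gap is 24 to 30 days from Day 2 and still 22 to 29 days from Days 3 to 4.
- A reader might infer lost second doses or damage to the efficacy conclusions. A dose missed through early tube collection is possible, but nothing suggests a rate. The Day 57 endpoint, the equivalence interval and the superiority tests do not use these grades.

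**What to change.** Set the lower limit of the Visit 2 window at Day 3 in Protocol 5.12.2, SAP section 3 and any schedule table that repeats it. Two forms work:
- **Day 3 (+1 day)**, Days 3 to 4, which matches the protocol's contents page. It leaves two permitted days instead of three and can collide with a weekend.
- **Day 3 (+2 days)**, Days 3 to 5, which keeps three permitted days and leaves a usable day after a Thursday baseline. Some visits would then be a day later than the present window allows.

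The second is easier for sites. Either is a one-line edit in each place. The cost is slightly less scheduling freedom or a slightly later early visit.

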5.12.3 Follow-up Phone Call /Day 15 (± 3 days)

- █ [REDACTED]
- █ [REDACTED]
- █ [REDACTED]
- █ [REDACTED]

5.12.4 Visit 3/Day 29 (± 3 days)

- █ [REDACTED]

5.12.5 Visit 4/Day 57 (± 2 days) End of Study /Early Termination Visit

- █ [REDACTED]

5.12.6 Unscheduled

An unscheduled visit is allowed at any time if in the investigator's opinion it is warranted. If the investigator assesses the subject's condition and determines that the subject's condition has worsened to the degree that it is unsafe for the subject to continue in the study, the subject may be discontinued from the study as a treatment failure, and a standard of care treatment

[REDACTED]

may be advised at the investigator's discretion. The following procedures may be performed at the Unscheduled/Early Termination Visit.

- [REDACTED]

5.13 Summary of Assessments

The schedule of visits and procedures to be conducted at each visit are summarized in the Schedule of Study Procedures.

| [REDACTED] |
|------------|------------|------------|------------|------------|------------|------------|
| [REDACTED] |
| [REDACTED] |
[REDACTED]	■					
[REDACTED]	■					
[REDACTED]	■					
[REDACTED]	■					
[REDACTED]	■					
[REDACTED]	■					
[REDACTED]	■				■	■
[REDACTED]	■	■		■	■	■
[REDACTED]	■	■	■	■	■	■
[REDACTED]	■	■	■	■	■	■

[REDACTED]						
[REDACTED]						
[REDACTED]						
[REDACTED]						
[REDACTED]						
[REDACTED]						
[REDACTED]						
[REDACTED]						

[REDACTED]

[REDACTED]

[REDACTED]

[REDACTED]

[REDACTED]

5.14 Screen Failures

A screen failure is a subject who received information about the study, including signing an informed consent/assent, and possibly performing some study related procedures but was not enrolled, dispensed and applied study medication. Screen failures information will not be entered in the database and will not be included in any data analyses.

5.15 Protocol Deviations/Violations

This study will be conducted as described in this protocol except for an emergency situation in which the protection, safety, and well-being of the subject requires immediate intervention, based on the judgment of the investigator or a responsible, appropriately trained and credentialed professional(s) designated by the investigator. In the event of a significant deviation from the protocol due to an emergency, accident or mistake, the investigator or designee must contact Perrigo/[REDACTED] contacts in Section 14 ([Appendix A](#)) at the earliest possible time.

[REDACTED]

[REDACTED]

[REDACTED]

[REDACTED]

[REDACTED]

[REDACTED]

[REDACTED]

Subjects with any variation from the protocol that would not interfere with the effect of or the accurate assessment of the assigned study treatment, may be included in both PP and mITT analyses.

5.16 Subject/Treatment Compliance

Subjects will apply the medication to the designated treatment area at approximately the same time once daily for 2 consecutive days. [REDACTED]

[REDACTED]. Compliance will be determined from the diary card, in which the subject will be instructed to record all applications made or missed. The first and last dates of treatment should be recorded in the source document and eCRFs. The total number of applied and missed applications should also be recorded. Applications will be considered missed if the study medication was not applied on Day 1 or Day 2 of the treatment period. Subjects will be considered compliant if they apply both daily doses on study Days 1-2. Subjects will be considered non-compliant if one (1) or more doses are missed. The study medication tube will be collected by the study site at appropriate visits or early termination.

5.17 Discontinuation/Withdrawal of Study Subjects

Subjects will be removed from the study for any of the following reasons:

- The subject withdraws his or her consent/assent for any reason.
- The subject's condition has worsened to the degree that the investigator feels it is unsafe for the subject to continue in the study.
- Subject did not meet entry criteria.
- The subject's medication code is unblinded.
- An adverse event (AE) including inter-current illness, occurs for which the subject desires to discontinue treatment or the investigator determines that it is in the subject's best interest to be discontinued.
- The subject is lost to follow-up. The investigator will document efforts to attempt to reach the subject twice by telephone and will send a certified follow-up letter before considering that subject lost to follow-up. All attempts must be thoroughly recorded.
- The subject becomes pregnant during the course of the trial.
- Lack of efficacy (treatment failure) (subject's own withdrawal or investigator removal from study)
- Investigator Discretion

[REDACTED]

Protocol No: PRG-NY-15-002

- Significant protocol violation or non-compliance with the study protocol that could interfere with the effect or accurate assessment of the assigned study treatment.

A subject will not be allowed to re-enroll in the study after they have been discontinued.

The reasons for a subject being discontinued will be documented in the source document, eCRFs and the enrollment log.

If a subject is discontinued from the study for any reason, the Visit 4/ Day 57 End of Study Visit/Early Termination Visit procedures should be completed and any outstanding data and study medication should be collected. Data, in addition to the primary reason for discontinuation and the date of removal, will be recorded in the source document and the End of Study eCRF.

[REDACTED]

[REDACTED]

6. MATERIALS AND SUPPLIES

6.1 Study Medication

The study medication supplied by Perrigo Israel Pharmaceuticals, Ltd. will consist of:

Test Product: Ingenol Mebutate Topical Gel 0.05%,
Perrigo New York, Inc. [REDACTED]

Reference Product: Picato® Topical Gel 0.05% (Ingenol Mebutate Topical Gel 0.05%),
manufactured by Leo Pharma Inc.

Vehicle: Vehicle of test product
Perrigo New York, Inc [REDACTED]

